### 3.3 Exclusion criteria

Subjects who meet any of the exclusion criteria are not to be enrolled in this study.

1. History of any of the following:
  - a. Clinically significant illness (other than HCV) or any other major medical disorder that may interfere with the participant treatment, assessment or compliance with the protocol; participants currently under evaluation for a potentially clinically significant illness (other than HCV) are also excluded.
  - b. History of chronic pulmonary disease associated with functional limitation, severe cardiac disease, major organ transplantation or other evidence of severe illness, malignancy, or any other conditions which would make the patient, in the opinion of the investigator, unsuitable for the study

- c. Solid organ transplant
  - d. Malignancy within 5 years prior to screening, with exception of specific cancers that may have been cured by surgical resection (basal cell skin cancer, etc.). Subjects under evaluation for possible malignancy are also excluded.
  - e. Significant drug allergy (such as anaphylaxis or hepatotoxicity).
2. Subject has a known or documented prior history of cirrhosis.
  3. Subject shows evidence of significant liver disease in addition to hepatitis C, which may include but is not limited to drug- or alcohol-related cirrhosis, autoimmune hepatitis, hemochromatosis, Wilson's disease, non-alcoholic steatohepatitis (NASH), or primary biliary cirrhosis
  4. Any of the following lab parameters at screening:
    - a. Direct bilirubin > 1.5 x ULN
    - b. Platelets < 50,000/ $\mu$ L
    - c. Creatinine clearance (CLcr) < 50 mL/min
    - d. Haemoglobin < 10 g/dL
    - e. Albumin < 30g/L
    - f. International Normalised Ratio (INR) >1.5 (unless subject is on a stable anticoagulant regimen or has known coagulopathy)
  5. Pregnant or nursing female.
  6. Use of prohibited concomitant medications as described in section 5.2
  7. Chronic use of systemically administered immunosuppressive agents (e.g. prednisone equivalent > 10 mg/day)
  8. Known hypersensitivity to velpatasvir, sofosbuvir or formulation excipients.
  9. Therapy with any anti-neoplastic or immunomodulatory treatment (including supraphysiologic doses of steroids and radiation)  $\leq$ 6 months prior to the first dose of study drug.
  10. Any investigational drug  $\leq$ 6 weeks prior to the first dose of study drug.
  11. Previous failure of therapy with sofosbuvir or an NS5A inhibitor prior to the first dose of study drug.
  12. Ongoing severe psychiatric disease as judged by the treating physician.
  13. Frequent injecting drug use that is judged by the treating physician to compromise treatment safety.
  14. Inability or unwillingness to provide informed consent or abide by the requirements of the study.
  15. Prior enrolment within this study.

Subjects will be stratified by genotype/subtype, HIV status and primary or reinfection for analysis.

### 3.4 Definitions used to calculate Estimated Date of Infection

The estimated date of HCV infection will be determined using data obtained at the screening visit according to the following rules (Table 1):

**Table 1. Estimated duration of infection calculation rules**

| Category  | Estimated date of HCV infection   |
|---|---|
| Acute clinical HCV                                      | 6 weeks prior to onset of acute clinical symptoms   |
| Acute asymptomatic HCV ALT < 400 IU/L                   | Mid-point between last negative HCV antibody or HCV RNA and first positive HCV antibody or HCV RNA  |
| Acute asymptomatic HCV ALT > 400 IU/L                   | 6 weeks prior to the date of peak ALT unless the estimated date of infection is after the date of first HCV antibody positive test. Then, 6 weeks prior to the date of the first HCV antibody positive test |
| HCV antibody negative and HCV RNA positive at screening | 6 weeks prior to the screening date   |

The estimated date of HCV will then be used to determine the estimated duration of HCV infection.

## 4 Study design

[figure not shown]
### 4.1 Summary of study design

This study will be conducted as a phase III randomised, open-label, non-inferiority multicentre international trial.

A total of 250 people with recently acquired hepatitis C will be enrolled and randomised.

The number of participants with HCV/HIV coinfection enrolled to the study will be capped at 70% (or less than 175 participants) of the total study population. In addition, the number of participants with HCV reinfection enrolled to the study will be capped at 20% (or less than 50 participants) of the total study population.

The study consists of a screening phase (-12 to -4 weeks), treatment commencement from baseline, randomisation between week 5 and 6, treatment for another 6 weeks for those randomised to standard therapy (12 weeks of treatment) or end of treatment for those randomised to shortened treatment (6 weeks of treatment). All participants will then enter the follow-up phase (96 weeks) to evaluate treatment response and reinfection (Figure 1). Randomisation will be using blocks and will be stratified by study site and HIV status.

**Figure 1: Study Schema**

Participants who become re-viraemic following an end of treatment response will be followed monthly for six months. After completing the monthly follow-up visits, participants will continue to attend three monthly follow-up visits up to two years. Please see section 7 'Reinfection follow-up' for more details.

#### 4.2 Visit Schedule

All participants will complete screening, on-treatment and post-treatment assessments as outlined in the Schedule of Assessments in Section 6.0.

Screening assessments must be completed within 12 weeks prior to baseline. There must be a minimum of 4 weeks between screening and baseline.

Following screening, eligible participants will commence treatment. Between week 5 and week 6 of treatment, the participants will be randomised to either the shortened or standard treatment duration. On-treatment visits will be conducted at weeks 1, 2, 4 and 6 (end of treatment for participants on shortened treatment duration), weeks 8 and 10 (for participants on standard treatment duration only). Participants on standard treatment duration will attend end of treatment at week 12. For participants randomised to shortened treatment, follow-up visits will be conducted at week 10 (SVR4), week 18 (SVR12), week 30 (SVR24), week 42 (FU1), week 54 (FU2), week 66 (FU3), week 78 (FU4), week 90 (FU5) and week 102 (Termination). For participants randomised to standard treatment, follow-up visits will be conducted at week 16 (SVR4), week 24 (SVR12), week 36 (SVR24), week 48 (FU1), week 60 (FU2), week 72 (FU3), week 84 (FU4), week 96 (FU5) and week 108 (Termination).

### 4.3 Treatment Discontinuation Criteria

Study drug must be discontinued in the following instances:

- Unacceptable toxicity
- Pregnancy of female subject
- Significant protocol violation
- Participant request to discontinue for any reason
- Discontinuation of the study by the Kirby Institute, regulatory agencies or a Human Research Ethics Committee / Research Ethics Committee / Institutional Review Board

Participants who cease study medication will, wherever possible, continue to be followed up according to the protocol study plan. Participants may revoke consent for follow-up without jeopardizing their relationship with either their doctor or the UNSW. If a participant revokes consent then, if possible, all assessments scheduled for the final visit should be completed.

## 5 Treatment of participants

### 5.1 Sofosbuvir/velpatasvir dosage and administration

Participants will receive six or twelve weeks of open-label sofosbuvir/velpatasvir (400mg/100mg daily) in an oral once-daily fixed dose combination. Dose modifications are prohibited.

### 5.2 Study Drug Adherence and Drug Accountability

Therapy will be administered in two-weekly supply. Participants will be asked to return study medication every two weeks. Study drug will be reconciled using a pill count on all returned drug bottles.

Participants will also be required to complete an adherence questionnaire as described in section 6.2.

### 5.3 Prior and Concomitant Medications

Concomitant medication must be recorded in the source documents and eCRF from screening until the last dose of study medication.

The following medications are prohibited from **six weeks prior to the baseline visit** through to the end of treatment:

- Haematologic stimulating agents (e.g. erythropoiesis-stimulating agents [ESAs]; granulocyte colony stimulating factor [G-CSF]; thrombopoietin [TPO] mimetics)
- Chronic systemic immunosuppressant use including, but not limited to corticosteroids (prednisone equivalent of >10 mg/day for >2 weeks), azathioprine, or monoclonal antibodies (e.g. infliximab)

- Investigational agents or devices for any indication
- Drugs disallowed per prescribing information of SOF

Concomitant use of certain medications or herbal/natural supplements (inhibitors or inducers of drug transporters i.e. P-gp) with study drug may result in pharmacokinetic interactions resulting in increases or decreases in exposure of study drug or these medications.

Due to decreases in sofosbuvir or velpatasvir exposure, use of sofosbuvir/velpatasvir with potent P-gp and moderate or potent CYP inducers is not recommended (83-85).

The use of the "Disallowed" agents in **Table 2** is prohibited from 21 days prior to Baseline through to the end of treatment except Amiodarone which is prohibited from 60 days prior to Baseline through to the end of treatment.

Examples of representative medication which are prohibited or are used with caution are listed below:

**Table 2: List of Disallowed Medications**

| Drug Class                                | Agents Disallowed   | Use with Caution  |
|---|---|---|
| Acid Reducing Agents a         |   | H2-Receptor Antagonists a , Antacids a , Proton Pump Inhibitors a                            |
| Anticonvulsants b              | Carbamazepine, Oxcarbazepine, Phenobarbital, Phenytoin,   |   |
| Antimycobacterials b           | Rifabutin, Rifapentine, Rifampin  |   |
| Antiretrovirals                           | Efavirenz b  |   |
| Cardiac Medications c          | Amiodarone e ,   | Bosentan, Digoxin c , Diltiazem, Dronedarone, Olmesartan, Quinidine, Ranolazine, Telmisartan, Valsartan, Verapamil |
| Herbal/Natural Supplements b   | St. John's Wort, Echinacea, Milk Thistle (i.e. silymarin), Chinese herb Sho-Saiko-To (or Xiao-Shai-Hu-Tang) |   |
| HMG-CoA Reductase Inhibitors d |   | Atorvastatin, Fluvastatin, Lovastatin, Pitavastatin, Pravastatin, Rosuvastatin (≤10 mg/day), Simvastatin                      |
| Other                                     | Modafinil b , sulfasalazine e , methotrexate e                             |   |

a H2-receptor Antagonists must not exceed a dose of 20 mg famotidine or equivalent and can be taken simultaneously with SOF/VEL and/or staggered by 12 hours. Antacids that directly neutralize stomach acid (i.e. Tums, Maalox) may not be taken within 4 hours (before or after) of SOF/VEL administration. Proton Pump Inhibitors equivalent to omeprazole 20 mg can be taken simultaneously with SOF/VEL in the fed state.

b May result in a decrease in the concentration of study drugs

c May result in an increase in the concentration of study drugs and/or concomitant medications; monitor for signs and symptoms of digoxin toxicity

d Use with SOF/VEL may result in an increase in the concentration of HMG-CoA Reductase Inhibitors. Monitor for signs and symptoms of muscle weakness or myopathy, including rhabdomyolysis.

e60 day washout period applies.

Refer to <http://www.hep-druginteractions.org/> and product information for further data.

Should any participant need to initiate treatment with any excluded concomitant medication during the study, the Medical Monitor, [name] must be consulted prior to the initiation of any excluded medication. In the event that an excluded medication is initiated prior to discussion with [name], he must be made aware of the use of the excluded medication as soon as possible. [name] contact details are listed on the cover of this protocol.

## 6 Study procedures

### 6.1 Visits and Procedures

The following assessments must be conducted at study visits as per the schedule of assessments:

|                                     |  |
|-------------------------------------|--|
| Vital signs & physical measurements | body weight a , height a   |
| Biochemistry                        | Creatinine, glucose, sodium, chloride, and potassium, creatine kinase  |
| Liver Function Tests                | ALT, AST, GGT, total bilirubin, albumin, alkaline phosphatase, total protein   |
| Full Blood Count                    | Haemoglobin, haematocrit, White Blood Cells, platelets, neutrophils  |
| Clotting                            | INR  |
| HCV RNA                             | Must be quantitative at Screening  |
| HCV Genotype                        | Within 12 months prior to screening  |
| HAV Serology                        | Hepatitis A total Ab (IgG), Hepatitis A IgM  |
| HBV Serology                        | Anti-HBc, HBsAg  |
| HCG Pregnancy Test                  | For women of childbearing potential, a negative urine (or serum) HCG test at screening and baseline  |
| Questionnaires                      | Behavioural survey, abbreviated behavioural survey, adherence questionnaire, Health Outcomes Survey (EQ-5D), Long-Acting Hepatitis C Therapy Questionnaire |

a at screening only

The following assessments and procedures must be performed at each visit as specified below:

#### Initial screening period (Week -12 to Week -4)

- Informed consent
- Medical history
- FibroScan®
- Vital signs and physical examination
- HCV antibody
- HCV RNA and genotype (Local laboratory)
- LFTs, FBC and biochemistry
- Clotting - INR
- HIV antibody, HAV & HBV serology
- CD4/CD8 & HIV viral load (HIV positive participants only)
- Pregnancy test (females of child bearing potential only)
- Study behavioural questionnaire
- Concomitant medication
- Health outcomes survey (EQ-5D)
- Research specimen collection (EDTA plasma, whole blood & ACD Plasma/PBMCs)

#### Baseline visit (Week 0)

- Vital signs and physical examination
- HCV RNA (Local laboratory)
- LFTs, FBC and biochemistry
- Pregnancy test (females of child bearing potential only)
- Adverse Events
- Concomitant medication
- Abbreviated Behavioural questionnaire
- Long-Acting Hepatitis C Therapy Questionnaire\*
- Research specimen collection (EDTA plasma, whole blood & ACD Plasma/PBMCs)

\* The Long-Acting Hepatitis C Therapy Questionnaire aims to obtain participant interest and attitudes towards long-acting parenteral hepatitis C therapy. All currently enrolled participants will complete the Long-Acting Hepatitis C Therapy Questionnaire at their next scheduled visit.

#### **Week 1 (+/- 3 days)**

- LFTs, FBC and biochemistry
- Adverse Events
- Concomitant medication
- Research specimen (EDTA plasma & ACD Plasma/PBMCs)

#### **Week 2 (+/- 3 days)**

- LFTs, FBC and biochemistry
- Adherence questionnaire
- Adverse Events
- Concomitant medication
- Research specimen (EDTA plasma & ACD Plasma/PBMCs)
- SOF/VEL pill count

#### **Week 4 (+/- 3 days)**

- LFTs, FBC and biochemistry
- Pregnancy test (females of child bearing potential only)
- Adherence questionnaire
- Adverse Events
- Concomitant medication
- Research specimen (EDTA plasma & ACD Plasma/PBMCs)
- SOF/VEL pill count

#### **Between Week 5 and Week 6 – RANDOMISATION**

#### **Week 6 (+/- 3 days)**

For participants in the shortened treatment arm – complete the ETR visit.

For participants in the standard treatment arm complete the following assessments.

- LFTs, FBC and biochemistry
- Abbreviated Behavioural questionnaire
- Adherence questionnaire
- Adverse Events
- Concomitant medication
- Research specimen (EDTA plasma & ACD Plasma/PBMCs)
- SOF/VEL pill count

**Week 8 (+/- 3 days) and Week 10 (+/- 3 days) – STANDARD DURATION ONLY**

- LFTs, FBC and biochemistry
- Pregnancy test (females of child bearing potential only) – week 8 only
- Adherence questionnaire
- Adverse Events
- Concomitant medication
- Research specimen collection (EDTA plasma)
- SOF/VEL pill count

**End of Treatment (ETR) – Week 6 (Shortened treatment) or Week 12 (Standard treatment) (+/-3 days)**

- HCV RNA (Local laboratory)
- LFTs, FBC and biochemistry
- CD4/CD8 & HIV viral load (HIV positive participants only) – Standard treatment arm only
- Pregnancy test (females of child bearing potential only) – Standard arm treatment only
- Adverse Events
- Concomitant medication
- Abbreviated Behavioural questionnaire
- Adherence questionnaire
- Research specimen collection (EDTA plasma & ACD Plasma/PBMCs)
- SOF/VEL pill count

**Post Treatment Follow-up Visits**

**Post Treatment Week 4 (SVR4) - Week 10 (Shortened treatment) or Week 16 (Standard treatment) (+/- 3 days)**

- LFTs, FBC and biochemistry
- Pregnancy test (females of child bearing potential only)
- Adverse Events
- Research specimen collection (EDTA plasma & ACD Plasma/PBMCs \*)

\*To be collected in patients with suspected relapse/reinfection only

**Post Treatment Week 12 (SVR12) - Week 18 (Shortened treatment) or Week 24 (Standard treatment) (+/- 14 days)**

- FibroScan®
- HCV RNA (Local laboratory)
- LFTs, FBC and biochemistry
- CD4/CD8 & HIV viral load (HIV positive participants only)
- Abbreviated Behavioural questionnaire
- Health outcomes survey (EQ-5D)
- Research specimen collection (EDTA plasma & ACD Plasma/PBMCs \*)

\*To be collected in patients with suspected relapse/reinfection only

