## Schedule of Assessments

### Arm A: Short – 6 weeks

| Assessment/Procedure                                    | Screening#     | Baseline       | Study Treatment (weeks) |       |       |            | Follow-up (weeks) |                |                |                |                |                |                |                |                      |  |
|---|----------------|----------------|-------------------------|-------|-------|------------|-------------------|----------------|----------------|----------------|----------------|----------------|----------------|----------------|----------------------|--|
| Study week  | -12 to -4      | 0              | 1                       | 2     | 4     | 6
(ETR) | 10
(SVR4)      | 18
(SVR12)  | 30
(SVR24)  | 42
(FU1)    | 54
(FU2)    | 66
(FU3)    | 78
(FU4)    | 90
(FU5)    | 102
(Termination) |  |
| Visit Window (Days)                                     |                |                | +/- 3                   | +/- 3 | +/- 3 | +/- 3      | +/- 3             | +/- 14         | +/- 14         | +/- 28         | +/- 28         | +/- 28         | +/- 28         | +/- 28         | +/- 28               |  |
| Informed consent, medical history, physical examination | x              |                |                         |       |       |            |                   |                |                |                |                |                |                |                |                      |  |
| Patient demographics                                    | x              |                |                         |       |       |            |                   |                |                |                |                |                |                |                |                      |  |
| Vital signs & physical measurements                     | x              | x              |                         |       |       |            |                   |                |                |                |                |                |                |                |                      |  |
| Randomisation g                              |                |                |                         |       |       | x          |                   |                |                |                |                |                |                |                |                      |  |

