**Post Treatment Week 24 (SVR24) - Week 30 (Shortened treatment) or Week 36 (Standard treatment) (+/- 14 days)**

- FibroScan®
- HCV RNA (Local laboratory)
- LFTs
- CD4/CD8 & HIV viral load (HIV positive participants only)
- Abbreviated Behavioural questionnaire
- Research specimen collection (EDTA plasma & ACD Plasma/PBMCs \*)

\*To be collected in patients with suspected relapse/reinfection only

**Post Treatment Weeks - 42 (FU1), 54 (FU2), 66 (FU3), 78 (FU4) and 90 (FU5) – Shortened treatment or  
- 48 (FU1), 60 (FU2), 72 (FU3), 84 (FU4) and 96 (FU5) – Standard Treatment  
(+/- 28 days)**

- FibroScan®
- HCV RNA (Local laboratory)
- LFTs
- CD4/CD8 & HIV viral load (HIV positive participants only)
- Abbreviated Behavioural questionnaire
- Research specimen collection (EDTA plasma & ACD Plasma/PBMCs \*)

\*To be collected in patients with suspected relapse/reinfection only

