## 20 Abbreviations List

|                      |  |
|----------------------|--|
| ALT                  | Alanine Aminotransferase   |
| AST                  | Aspartate Aminotransferase   |
| DAA                  | Direct Acting Antiviral  |
| End of treatment     | Date of last dose of treatment   |
| ETR                  | End of Treatment Response, undetectable HCV RNA at the completion of treatment   |
| FBC                  | Full Blood Count (haemoglobin, WCC including differentials, platelets)   |
| HCV                  | Hepatitis C Virus  |
| HCV RNA re-viraemia  | Detection of the hepatitis C virus again following an end of treatment response  |
| HIV                  | Human Immunodeficiency Virus   |
| IDUs                 | Injection Drug Users   |
| INR                  | International Normalized Ratio   |
| LFTs                 | Liver Function Tests – albumin, ALT, AST, alkaline phosphatase, GGT, total bilirubin, total protein  |
| LLOQ                 | Lower Limit Of Quantification  |
| GGT                  | Gamma Glutamic Transpeptidase  |
| Hgb                  | Haemoglobin  |
| PEG-IFN              | Pegylated interferon alfa 2a   |
| PWID                 | People Who Inject Drugs  |
| Superinfection       | Detection of infection with an HCV strain which was distinct from the primary infecting strain in those with HCV virological persistence   |
| Reinfection          | Detection of infection with an HCV strain which was distinct from the primary infecting strain among participants with either spontaneous or treatment-induced HCV virological suppression ( $\leq 15$ IU/ml on Roche TaqMan). |
| RAV                  | Resistance-associated variants   |
| RVR                  | Rapid Virological Response, HCV RNA undetectable at week 4 of treatment  |
| vRVR                 | Very Rapid Virological Response, HCV RNA undetectable at week 2 of treatment   |
| SOF                  | Sofosbuvir   |
| SVR4                 | Sustained Virological Response, HCV RNA undetectable 4 weeks post-treatment  |
| SVR12                | Sustained Virological Response, HCV RNA undetectable 12 weeks post-treatment   |
| SVR24                | Sustained Virological Response, HCV RNA undetectable 24 weeks post-treatment   |
| TND                  | Target not detected (HCV RNA below the level of quantitation)  |
| TDnq                 | Target detected, not quantifiable (HCV RNA detected but not quantifiable)  |

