The modified Intention to Treat (mITT) population includes participants in the FAS excluding those with non-virological reasons for treatment failure (i.e., death, loss to follow up) and reinfection. Participants with confirmed reinfection after achieving an ETR, but prior to the primary efficacy endpoint (SVR12), will be excluded from the mITT.

Per-protocol Analysis Set

The PP population is defined as all participants who received >90% of scheduled treatment for >90% of the scheduled treatment period with follow-up virologic data to SVR12.

Safety Population

The Safety population includes all participants who randomised and will be analysed and presented according to the actual on-treatment monitoring arm received during the study.

The ITT population will be used for primary efficacy analyses, and the safety population will be used for all safety analyses.

Data Handling Conventions

Missing Data

For the analyses of categorical HCV RNA data, missing post-treatment HCV RNA data will have the missing data imputed. Missing on-treatment HCV RNA will have the missing data imputed up to the time of the last dose.

If a data point is missing and is preceded and followed in time by values that are "<LLOQ, TND," then the missing data point will be set to "<LLOQ, TND."

If a data point is missing, and preceded and followed by values that are "<LLOQ, target detected," or preceded by "<LLOQ, target detected" and followed by "<LLOQ, TND," or preceded by "<LLOQ, TND" and followed by "<LLOQ, target detected," then the missing value will be set to "<LLOQ, target detected."

If a data point is missing, and preceded and followed by values that are ">LLOQ, target detected," or preceded by ">LLOQ, detected" and followed by "<LLOQ, target detected" or "<LLOQ, TND", then the missing value will be set to ">LLOQ, target detected."

The following scenarios describe a framework for analysis of the primary endpoint based on various anticipated events for the ITT and mITT population:

- i. In the event of the participant dying or becoming lost to follow-up prior to SVR 12, the participant will be considered to have failed treatment (loss to follow up = failure)
- ii. If the SVR 12 time-point measure is missing, then the next available measure (i.e., SVR 24 or later) will be used. If no future time points are available, the participant will be considered a treatment failure.

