In general, the baseline value will be the last non-missing value on or prior to the first dose date of study drug. HCV RNA and safety laboratory data collected up to the last dose date + ≤ 3 days are considered to be on-treatment data. HCV RNA and safety laboratory data collected after the last dose date + >3 days are considered post-treatment data. HCV RNA and safety laboratory data collected after the last dose date + >3 days will be assigned to the post-treatment follow-up (FU) visits. Visit windows will be calculated from the last dose date (ie, FU Day = collection date minus the last dose date) as shown.

Table 1. On-treatment visit analysis windows

Nominal visit	Nominal day	Lower Limit	Upper Limit
	Baseline	1	NA
Week 2	14	8	21
Week 4	28	22	35
Week 6*	42	36	49
Week 8	56	50	63
Week 10	70	64	77
Week 12	84	78	≥ 85

*Shortened arm ETR

Table 2. Post-treatment visit analysis windows

Nominal FU visit	HCV RNA			Safety Laboratory Data		
	Nominal day	Lower Limit	Upper Limit	Nominal day	Lower Limit	Upper Limit
PT week 4	28	21	69	28	4	30
PT week 12	84	70	146	NA	NA	NA
PT week 24	168	147	NA	NA	NA	NA

PARTICIPANT DISPOSITION

Recruitment

The following dates will be presented to define the period of recruitment and follow-up:

- I. first and last participant screened
- II. first and last participant baselined
- III. first and last participant to complete PT week 12

Participant Enrolment and Disposition

A summary of participant enrolment will be provided- overall and by treatment group (if appropriate). The total number of participants who were screened, enrolled and treated will be depicted by a flowchart (**Figure 2**).

A summary of participant disposition will be provided overall (**Table 3**).

Reasons for participant exclusion, including screen failure and loss to follow up, will be summarised (**Table 4, Table 5**).

Protocol violations

Number, proportion, type and reason for any protocol violations will be described (**Table 6**).

Figure 2. Participant disposition

[figure not shown]

Table 3. Recruitment and follow-up

Participant disposition	Total N (%)	Standard arm N(%)	Shortened arm N(%)

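### The protocol dates SVR12 by study week and the SAP by days from last dose with no slack, so a compliant SVR12 sample can, at the margin, be assigned to post-treatment week 4

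*Protocol*

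**What the plan says.** **Protocol.** The synopsis and section 4.2 put SVR12 at study week 18 (6-week arm) or 24 (12-week arm). The Arm A schedule lists week 18 in a row labelled as study week. Section 6.1 heads the visit "Post Treatment Week 12 (SVR12) - Week 18 (Shortened treatment) or Week 24 (Standard treatment) (+/- 14 days". The end-of-treatment visit is "End of Treatment (ETR) – Week 6 (Shortened treatment) or Week 12 (Standard treatment) (+/-3 days". The abbreviations list in section 20 defines end of treatment as "Date of last dose of treatment". Section 4.3 says of early stoppers: "Participants who cease study medication will, wherever possible, continue to be followed up according to the protocol study plan".

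In the Arm A schedule, the row "Visit Window (Days" shows ±14 at week 18, which agrees with section 6.1. The same row for Arm B, as read from the PDF, shows ±3 at week 24.

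**SAP.** Under Analysis Windows: "Visit windows will be calculated from the last dose date (ie, FU Day = collection date minus the last dose date) as shown". Table 2 gives these HCV RNA windows in FU days: post-treatment (PT) week 4, 21 to 69; PT week 12, 70 to 146; PT week 24, 147 onwards. Under Missing Data, scenario ii: "If the SVR 12 time-point measure is missing, then the next available measure (i.e., SVR 24 or later) will be used". If nothing later is available, the participant counts as a treatment failure. The SAP has no rule for two results in one window.

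**The concern.** Study week 18 or 24 and 12 weeks after last dose are the same date only when the last dose falls on the nominal day. The protocol does not say which governs when it does not. The SAP's lower limit fits only if the ±14 days run from the last dose.

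Two things are at stake.

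1. **A late last dose.** A sample that meets the visit schedule may be filed as PT week 4, so the SVR12 value is treated as missing and replaced. A later result can bring in a reinfection acquired after week 12. A suppressed participant with no later sample would be scored as a failure.
2. **An early stop in the 12-week arm.** On a study-week schedule, SVR12 is taken later after last dose than in the 6-week arm. Reinfections are removed from the mITT set but not from the ITT set. The extra time at risk would therefore sit in the control arm of a non-inferiority comparison, where a lower control rate favours the short course.

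**Working it through.** Days are counted from baseline = day 0.

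**1. The SAP's own limits.** The interval from nominal end of treatment to SVR12 is (18 − 6) × 7 = 84 days, and (24 − 12) × 7 = 84 days. Then 84 − 14 = 70. Both figures match Table 2 (nominal 84, lower limit 70). The limit equals the edge of the visit window exactly.

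**2. Late last dose, 6-week arm.** Week 18 is day 126, so the ±14-day window runs from day 112 to day 140, which is 29 days.

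| Last dose | FU days of compliant visits | Days in PT week 4 window |
|---|---|---|
| day 42 | 70 to 98 | 0 of 29 |
| day 43 | 69 to 97 | 1 of 29 (3.4%) |
| day 44 | 68 to 96 | 2 of 29 (6.9%) |
| day 45 | 67 to 95 | 3 of 29 (10.3%) |

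Under the section 6.1 window the 12-week arm gives the same result: week 24 is day 168, and 168 − 14 = 154. A last dose on day 85, 86 or 87 puts day 154 at FU 69, 68 or 67. Under ±3 days the earliest visit is day 165. Even a last dose 7 days late (day 91) then gives FU 74, so nothing is misassigned.

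**3. Uninterrupted dosing.** Forty-two daily tablets from day 0 end on day 41. The earliest visit is then FU 112 − 41 = 71, one day inside the window.

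**4. Is a replacement available?** In the 6-week arm SVR24 is week 30 (day 210) ±14, so day 196 to 224. With a last dose on day 45 that is FU 151 to 179, inside the PT week 24 window.

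**5. Early stop, 12-week arm.** Suppose the last dose is on day 42 and visits stay on study weeks.
- The week 24 visit is at FU 168 − 42 = 126, which is 18 weeks after last dose.
- The week 16 visit (day 112 ± 3) is at FU 67 to 73. On 4 of its 7 permitted days (70 to 73) it is also in the 70 to 146 window.
- Plasma is collected at week 16, and the SAP has HCV RNA assessed centrally at all scheduled visits, so both results should exist.
- In the 6-week arm randomisation falls between weeks 5 and 6, so a randomised participant can stop only about a week early. That gives 84 + 7 = 91 days, or 13 weeks.

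**6. After re-anchoring.** If the visit is 84 ± 14 days from the actual last dose, every compliant sample is at FU 70 to 98. All 29 days are then in the PT week 12 window.

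**The case against.** **The protocol can be read as counting from last dose.** The visit is titled post-treatment week 12, the endpoint is 12 weeks after end of treatment, and end of treatment is the date of last dose. The limit of 70 suggests that the SAP's authors read it this way. This has force, but the synopsis, section 4.2 and the Arm A schedule give only study weeks. The anchor is therefore unstated, not settled. For the same reason, early stoppers staying on study weeks is only one reading of section 4.3.

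**The ±3 days at end of treatment is a visit window, not a dosing window.** Correct. Supply is two-weekly in bottles of 14, and an uninterrupted course leaves a day to spare. Misassignment needs an interrupted or delayed course together with a visit at the extreme early edge.

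**Inferences that go too far.**
- A reader might infer that the primary endpoint becomes missing. It does not: scenario ii substitutes SVR24 or later, and failure is scored only when nothing later exists.
- A reader might infer a rate. Taking the last-dose day as uniform over days 39 to 45 and the visit as uniform over its 29 days gives (1 + 2 + 3)/(7 × 29) = 6/203 = 3.0%. Days 38 to 44 give 3/203 = 1.5%, and no last dose after day 42 gives zero. The documents support none of these distributions, so they are not estimates.
- A reader might infer that both arms are equally exposed. That depends on which Arm B window applies. The ±3 may come from the PDF reading: the row's two ±14 entries fall on weeks 36 and 48, whereas section 6.1 has ±14 at weeks 24 and 36.

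**The SAP postdates the DSMB recommendation to end the short arm.** Rescheduling visits therefore does little for data already collected. Widening the primary window now would change an endpoint rule late in an open-label trial. This stands and limits the fix.

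**Conclusion.** The two documents use different anchors for the primary endpoint visit, and the SAP's lower limit leaves no room for the difference. A sample that complies with section 6.1 can be assigned to PT week 4 when the last dose is 1 to 3 days after day 42 (or day 84 under ±14 days) and the visit is at the early edge of its window. SVR12 is then substituted, or scored as failure if no later sample exists.

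The effect is small. No sample is misassigned when dosing ends on schedule. The frequency of late last doses is not given, so the number affected cannot be computed. Reassignment also changes an outcome only if the later result differs or is absent. One changed outcome moves an arm's SVR12 by 1/99 = 1.0 or 1/93 = 1.1 percentage points, against a 12-point margin.

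The early-stopper point is real but narrow. It needs a 12-week participant who stops around week 6 and the study-week reading of section 4.3. The absence of a rule for two results in one window holds on either reading. The FU1–FU5 heading, "Post Treatment Weeks - 42 (FU1), 54 (FU2), 66 (FU3), 78 (FU4) and 90 (FU5", labels study weeks as post-treatment weeks and is a clerical slip.

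**What to change.** 1. In protocol sections 4.2 and 6.1, schedule SVR4, SVR12 and SVR24 from the actual last-dose date, including after early stopping, and give study weeks as nominal only.
2. Reconcile the Arm B visit window at week 24 with section 6.1, and relabel FU1–FU5 as study weeks.
3. In the SAP, state that when two results fall in the PT week 12 window, the one nearest FU day 84 is used. In the early-stop example, the week 16 result at FU 70 (14 days away) would be chosen over week 24 at FU 126 (42 days away).
4. For data already collected, leave the primary window unchanged. Count nominal SVR12 samples at FU days 67 to 69 as SVR12 only in a stated sensitivity analysis, and report how many there are.

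The cost is wording in both documents and one small additional analysis. Item 1 would have most value for visits still to be scheduled. Items 3 and 4 matter for results already in hand.
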